#### ***Handling of medication missing/partial dates***

No imputation of medication start/end dates or times will be performed. If a medication date or time is missing or partially missing and it cannot be determined whether it was taken prior or concomitantly, it will be considered a prior, concomitant, and posttreatment medication.

#### ***Handling of adverse events with missing or partial date/time of onset***

In case of missing or inconsistent information, an adverse event (AE) will be counted as a treatment-emergent adverse event (TEAE), unless it can clearly be ruled out that it is not a TEAE (eg, by partial dates or other information).

If the start date of an AE is incomplete or missing, it will be counted as TEAE except if an incomplete date indicates that the AE started prior to treatment.

No imputation of adverse event end dates/times will be performed. These data imputations are for categorization purpose only and will not be used in listings. No imputation is planned for date/time of adverse event resolution.

#### ***Handling of adverse events when date and time of first investigational medicinal product administration is missing***

When the date and time of the first IMP administration is missing, all adverse events that occurred on or after the day of enrollment should be considered as treatment-emergent adverse events. The exposure duration should be kept as missing.

The last dose intake should be clearly identified in the case report form and should not be approximated by the last returned package date.

## ***Handling of missing assessment of relationship of adverse events to investigational medicinal product***

If the assessment of the relationship to IMP is missing, then the relationship to IMP has to be assumed and the adverse event considered as such in the frequency tables of possibly related adverse events, but no imputation should be done at the data level.

## ***Handling of missing severity of adverse events***

No imputation of the severity of AEs will be performed.

### **2.5.4 Windows for time points**

The time window is defined as below to create analysis visit. The relative day below is referred to the first dose intake in the EFC13781 study. The end of study is defined as patient completed at least 2 years of follow-up (unless early discontinuation) up to 4 years or early discontinued from the study or until commercial eliglustat is available to the patients. Thus, the analysis visit list may be longer than the list below. The same algorithm will be applied to the trailing visits after the Week 416 if applicable.

**Table 2 - Analysis visit schedule**

Analysis visit	Target day	Schedule A	Schedule B	Schedule C	Schedule D
Baseline	1	[-45, 1]	[-45, 1]	[-45, 1]	[-45, 1]
Week 26	182	[2, 272]		[2, 272]	
Week 52	364	[273, 454]	[2, 545]	[273, 454]	
Week 78	546	[455, 636]		[455, 636]	
Week 104	728	[637, 818]	[546, 909]	[637, 818]	[2, 1091]
Week 130	910	[819, 1000]		[819, 1000]	
Week 156	1092	[1001, 1182]	[910, 1273]	[1001, 1182]	
Week 182	1274	[1183, 1364]		[1183, 1364]	
Week 208	1456	[1365, 1546]	[1274, 1637]	[1365, 1546]	[1092, 1819]
Week 234	1638	[1547, 1728]		[1547, 1728]	
Week 260	1820	[1729, 1910]	[1638, 2001]	[1729, 1910]	
Week 286	2002	[1911, 2092]		[1911, 2092]	
Week 312	2184	[2093, 2274]	[2002, 2365]	[2093, 2274]	[1820, 2547]
Week 338	2366	[2275, 2456]		[2275, 2456]	
Week 364	2548	[2457, 2638]	[2366, 2729]	[2457, 2638]	
Week 390	2730	[2639, 2820]		[2639, 2820]	
Week 416	2912	[2821, 3002]	[2730, 3093]	[2821, 3002]	[2548, 3275]

Note: Target day is calculated as number of week times 7 days.

The relative day is calculated as date of assessment - first eliglustat administration date in EFC13781 + 1.

Schedule A should be applied to complete physical examination and blood pregnancy test.

Schedule B should be applied to Gaucher disease clinical assessment, DXA, MRI (femur, lumbar, spleen, liver) assessment.

Scheduled C should be applied to QOL (SF36), Biomarkers and Hematology assessment.

Scheduled D should be applied to X-ray (femurs, lumbar spine) assessment.

Analysis flag will be generated to ensure only one assessment per parameter per analysis visit time window can be included in the analysis. The assessment closest to the targeted visit date will be used in the presence of multiple measurements within the same time window. When there are multiple measurements have the same distance compare to the target day, then scheduled visit should be selected first, than unscheduled visit can be considered. If there is still “tie” situation, we will choose the later one.

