10.2.3.3 Special provision for URM patients

CYP2D6 URM patients will have liver and spleen MRI and hematology performed every 6 month till week 52. However, the frequency of liver and spleen MRI and hematology can be increased to every 3 month till week 52 at the discretion of the Investigator. After week 52 CYP2D6 URMs patients will follow the standard schedule.

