10.2.5.3 Imaging

- X-Ray femur and spine, unless it was performed less than 2 years prior
- DXA hip and spine, unless it was performed less than 1 year prior
- Bone MRI, unless it was performed less than 1 year prior
- Liver and spleen MRI, unless it was performed less than 1 year prior

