#### **2.4.4 Analyses of efficacy endpoints**

In reference to the study period, efficacy result will be evaluated for all patients at the 2 year point by measured values (eg, category of bone pain, or bone density value in g/cm^2) and changes from baseline (eg, shift in category of bone pain or absolute and percent change from baseline in BMD g/cm^2 or incidence over 2 years, as appropriate).

In reference to the period of eliglustat treatment, efficacy result will be evaluated 2 years after study entry, but results will be grouped by duration of eliglustat treatment at the time of analysis. The actual groupings will depend on the distribution of treatment duration at the time of analysis (eg,  $\leq 5$  years versus  $>5$  years).

When the study has completed, summaries will be performed comparing to the 2 baselines as described above if applicable.

All efficacy endpoints will be summarized descriptively; no hypothesis testing will be performed. In general, descriptive statistics (number, mean, standard deviation, minimum and maximum) of the absolute value, change from baseline and/or percentage change from baseline for continuous endpoints will be analyzed. Summary statistics (count, percentage) will be summarized for the categorical endpoints. Cumulative incidence (n, percentage), incidence rate (n/year), or other descriptive statistics will also be displayed as appropriate. Calculations and summaries will include all non-missing data at a given time point, imputation will not be performed.

By-patient data listings containing efficacy endpoints will be produced if necessary.

All the below mentioned other efficacy endpoint analyses will be produced for the full analysis population. Refer to [Section 2.5.3](#) for details on handling dropouts, missing data, and patients who have more than one value assessed within the same time frame.

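### SAP Table 2 has no place for the Week 26 liver/spleen MRI that the protocol requires in CYP2D6 ultra-rapid metabolizers, so that scan drops out of the by-visit summary or is labelled Week 52

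*SAP*

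**What the plan says.** Protocol 10.2.3.3, repeated in the note under the flow chart, sets a special schedule: "CYP2D6 URM patients will have liver and spleen MRI and hematology performed every 6 month till week 52". The investigator may increase this to every three months. SAP 2.1.3.3 mentions the three-monthly option for URM volume scans but not the six-monthly minimum, and SAP Table 1 lists the scans as yearly with no URM exception. SAP 2.4.4.4 promises spleen and liver volumes by visit, with URM patients analysed separately.

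SAP 2.5.4, Table 2, assigns assessments to visits. For imaging and clinical assessments it says: "Schedule B should be applied to Gaucher disease clinical assessment, DXA, MRI (femur, lumbar, spleen, liver) assessment". Schedule B has no Week 26 row; its first post-baseline window is Week 52, [2, 545]. Two rules then apply: "Analysis flag will be generated to ensure only one assessment per parameter per analysis visit time window can be included in the analysis" and "The assessment closest to the targeted visit date will be used in the presence of multiple measurements within the same time window".

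Table 2 has no row for an exit visit. SAP 2.4.4 refers to 2.5.3 for dropouts and multiple values, but 2.5.3 contains nothing that overrides Table 2. Protocol 10.2.5 requires mobility, bone pain and bone crisis, SF-36 and biomarkers at discontinuation with no waiver for recent results. Imaging does have a waiver, for example: "DXA hip and spine, unless it was performed less than 1 year prior".

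**The concern.** The protocol adds a six-month volume scan for URMs because experience with them is limited (Protocol 8.1). Its introduction also reports that the one URM treated in one of the Phase 3 studies did not respond. The SAP intends to show URM volumes by visit, but its windowing rule allows only one year-1 value. The six-month result, the earliest protocol-required look at volume in this subgroup, has no row to appear in.

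The mislabelling case matters more than the omission. If a URM patient leaves the study between Week 26 and Week 52, the exit liver/spleen MRI is waived because the Week 26 scan is less than a year old. The Week 26 scan is then the only value in the window and is tabulated as a one-year result. Protocol 7.3 names clinically significant increases in liver or spleen volume as an example of decline that may warrant leaving the study, so this is a plausible route.

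A lesser issue comes from the same table. Because the earliest window opens at Day 2, clinical assessments from a very early exit can be counted in the Week 52 row.

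**Working it through.** **Inputs.** Target days: "Target day is calculated as number of week times 7 days". Day count: "The relative day is calculated as date of assessment - first eliglustat administration date in EFC13781 + 1". Windows are from SAP Table 2. Visit tolerance is ±14 days (Protocol 10.2.3 and 10.2.4).

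**1. Reproduce Table 2.** Targets are 26 × 7 = 182, 52 × 7 = 364 and 104 × 7 = 728. Take upper bound = target + half the visit interval − 1, and lower bound = end of the previous window + 1, with baseline ending at Day 1.

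| Schedule, visit | Lower | Upper | Table 2 |
|---|---|---|---|
| C, Week 26 | 1 + 1 = 2 | 182 + 91 − 1 = 272 | [2, 272] |
| C, Week 52 | 272 + 1 = 273 | 364 + 91 − 1 = 454 | [273, 454] |
| B, Week 52 | 1 + 1 = 2 | 364 + 182 − 1 = 545 | [2, 545] |
| B, Week 104 | 545 + 1 = 546 | 728 + 182 − 1 = 909 | [546, 909] |
| D, Week 104 | 1 + 1 = 2 | 728 + 364 − 1 = 1091 | [2, 1091] |

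This rule fits all 28 distinct windows (16 for A and C, which are identical, 8 for B, 4 for D).

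**2. Place the URM scans under Schedule B.** The Week 26 scan falls on Days 168 to 196 and the Week 52 scan on Days 350 to 378. Both lie in [2, 545].

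- Week 26 scan: smallest distance to target = 364 − 196 = 168 days.
- Week 52 scan: largest distance = 378 − 364 = 14 days.

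The Week 26 scan loses in every case. A visit exactly 26 or 52 weeks after Day 1 is relative Day 183 or 365. Counting that way gives 364 − 197 = 167 against 379 − 364 = 15, with the same outcome.

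**3. Week 52 scan missing.** The Day 182 scan is then alone in [2, 545] and is reported as Week 52, 182 days before the target.

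**4. Three-monthly option.** Scans on Days 91, 182, 273 and 364 all fall in [2, 545]. One is kept and three are dropped.

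**5. Same scans on the 26-week windows.** Day 182 goes to Week 26 and Day 364 to Week 52, so both required scans are kept. On the three-monthly option Day 91 shares Week 26 with Day 182, and Day 273 shares Week 52 with Day 364, so two of four are still dropped.

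**6. Very early exit, for example Day 30.** Day 30 lies in [2, 545], so mobility, pain and crises become Week 52. It also lies in [2, 272], so biomarkers and SF-36 become Week 26. This happens only if no later value falls in the window. If the previous Gaucher assessment was done in screening (Day −45 to −1), the crisis count covers about 31 to 75 days (30 + 1 to 30 + 45), against about a year for other patients in the row.

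**7. Exit imaging.** Add the one-year waiver to the baseline scan day. A scan at Day −45 gives −45 + 365 = Day 320, and a scan at Day −1 gives Day 364. An earlier exit scan needs a baseline scan carried over from the parent study; a scan at Day −200, for instance, allows an exit scan from Day 165. Even then about a year separates the two scans. For X-ray the waiver is two years. With the oldest allowed carry-over (about Day −45 − 365 = −410), the earliest exit X-ray is about −410 + 730 = Day 320.

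**The case against.** The case for leaving the table alone is fair on several points. Organ volume is an additional endpoint in SAP 2.1.3.3, neither primary nor secondary. The protocol gives patient care, not a Week 26 table, as the reason for extra URM monitoring. The unselected scan stays in the database and may be listed, and URM Week 26 hematology is on Schedule C and is reported. The study is descriptive: "All efficacy endpoints will be summarized descriptively; no hypothesis testing will be performed". URMs will be few. All of this limits the size of the problem. It does not remove the mismatch, because the SAP itself commits to by-visit volumes for URMs and then gives the required visit no row. The exception in SAP 2.5.5 for unscheduled repeat volume assessments does not help: it admits the value to by-visit summaries but creates no Week 26 window.

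A reader might infer that the Day 2 start is an error against the table's own spacing. The documents do not support that. A symmetric half-interval rule fits 25 of the 28 windows, but Table 2 never states it, and the contiguous rule in step 1 fits all 28. Moving the start to Day 182 (Schedule B) or Day 91 (A and C) would leave unassigned days and is partly a preference. It would not rescue the URM scan either, since Day 182 would still sit in [182, 545] and lose to Day 364.

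A reader might also infer that exit DXA and bone MRI put near-baseline values into the Week 52 row. The waiver rules that out (step 7).

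Very early exits should also be rare. Patients enter after about 4 to 8 years on eliglustat, and those who stop treatment are meant to be followed to scheduled completion.

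**Conclusion.** The URM point holds. Under Table 2 as written, the Week 26 liver/spleen MRI never reaches the by-visit URM summary as a Week 26 value. It is dropped when a Week 52 scan exists and labelled Week 52 when none does. That is one of two required post-baseline scans in year 1 for each URM, or three of four on the optional schedule. The documents do not say how many URMs will enrol. The protocol introduction mentions five treated in two Phase 3 studies; if one to five enrolled and completed year 1, one to five required scans would be lost from the table. The result assumes scans within ±14 days of schedule and Table 2 applied literally.

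The exit-visit point is secondary and minor. It covers mobility, bone pain and crisis counts on Schedule B, and biomarkers and SF-36 on Schedule C, in patients who leave very early with no later value in the window. Each such patient is about 1/32 = 3% of a visit's denominator at the planned size; the documents give no expected number. Schedule D shares the Day 2 start, but the X-ray waiver leaves little room for a very early value. The Week 104 windows of Schedules A, B and C, which serve the two-year evaluation, are unaffected.

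**What to change.** 1. In SAP Table 2, take liver/spleen MRI in CYP2D6 URM patients off Schedule B through Week 52 and apply the 26-week windows: Week 26 [2, 272] and Week 52 from Day 273. Schedule C's Week 52 window closes at Day 454 and Schedule B's Week 104 window opens at Day 546, so run the URM Week 52 window on to Day 545; otherwise Days 455 to 545 (91 days) belong to no visit. Use Schedule B from Week 104.
2. Bring SAP Table 1 and 2.1.3.3 into line with Protocol 10.2.3.3 on URM scan frequency, and list every URM volume by actual study day, so that optional three-monthly scans can be seen even though the table still thins them.
3. State how discontinuation-visit values are labelled. Either flag very early exit values within the by-visit rows or show them in a separate exit row, and give the interval covered by each crisis count. Apply the same rule to Schedule D. Keep these values in the report, since repeated bone crises are among the reasons a patient may be withdrawn.

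The cost is a SAP edit and some programming, with no change to conduct or data collection. The downside is a small extra row describing few patients.

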Expected number of sites:	Approximately 4 sites
STUDY TREATMENT(s)	
Investigational medicinal product(s)	Eliglustat
Formulation	Eliglustat is supplied as 84 mg hard gelatin capsules. Each 84 mg capsule contains 100 mg eliglustat tartrate, which is equivalent to 84 mg eliglustat free base
Route(s) of administration	Oral
Dose regimen	Cytochrome P450 2D6 (CYP2D6) IMs, EMs and URM will be treated with 84 mg twice daily (BID). CYP2D6 PMs will be treated with 84 mg once daily (QD).
Noninvestigational medicinal product(s) (if applicable)	N/A
Formulation	
Route(s) of administration	N/A
Dose regimen	N/A
ENDPOINT(S)	Primary endpoint The main purpose in this extension study is to evaluate long term skeletal response to eliglustat, i.e., change in bone disease after 2 years of additional treatment with eliglustat. The elements of bone disease to be evaluated include bone pain, bone crisis, mobility, bone marrow infiltration, bone mineral density (BMD), lytic lesions, infarcts, fractures, osteonecrosis, and bone biomarkers (Procollagen type I N-terminal propeptide (P1NP; bone formation) and C-terminal telopeptide (CTX; bone resorption), and macrophage inflammatory protein-1 beta (MIP-1 β). These efficacy assessments will be collected at baseline and thereafter at twice-yearly (bone biomarkers) or yearly (pain, crisis, mobility, bone marrow infiltration, bone mineral density, lytic lesions, infarcts, fractures) intervals. Secondary endpoint(s) Evaluation of patients' quality of life (Short Form-36 Health Survey) and biomarkers of GD1 (chitotriosidase, plasma GL-1 and lyso-GL-1). Quality of Life (QOL) and biomarkers of GD1 will be performed at baseline and twice yearly. The safety of eliglustat (i.e., incidence of (S)AEs, concomitant medications, changes from study baseline in physical examinations, routine laboratory assessments (hematology) and pregnancy testing for female patients of childbearing potential). Safety assessments will be performed at baseline and twice yearly. Continuous monitoring will be performed for (S)AEs and

	concomitant medications.

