STATISTICAL CONSIDERATIONS	
Sample size determination:
 
This study will enroll all eligible patients having successfully completed one of the Phase 2 or Phase 3 trials (approximately 32 patients).
 
Analysis population:
 
Efficacy analyses will be performed on the Full Analysis Set (FAS) population, defined as all patients who enroll in this study and who received at least 1 dose of eliglustat treatment in this study.
 
Safety analyses will be performed on the Safety Set, which is equivalent to the FAS for this study.
 
Primary analysis:
 
Analysis will be performed at two time points in this study. The main analysis will be performed after all patients have completed the 2 year assessments (two-year analysis period). An additional analysis will be performed upon study completion. For both efficacy and safety outcomes summary statistics will be calculated and presented. Hypothesis testing will not be performed.
 
For bone disease outcomes, summary statistics as well as cumulative incidence and incidence rates will be calculated, as appropriate. For continuous variables, change from study baseline as well as change from eliglustat baseline, defined as the change from first dose of eliglustat in the Phase 2 or 3 study, will be presented. Incidence and incidence rates will also be calculated separately, from study baseline and eliglustat baseline.
 
Analysis of secondary endpoints:
 
Quality of Life assessments, physical examinations, hematology, biomarkers and pregnancy testing for female patients of childbearing potential will be summarized at each time point. Additionally, the change from study baseline and eliglustat baseline (1st dose received in the previous study) will be summarized, as appropriate. Adverse experience will be coded using the Medical Dictionary for Regulatory Activities (MedDRA) Version 18.0 or higher. All adverse experiences will be summarized by body system and MedDRA preferred term (PT) overall, by relationship and severity and seriousness. All deaths will be summarized. Concomitant medications will be reported.

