#### **2.1.3.1.1 Gaucher disease clinical assessments (mobility, bone pain, bone crisis)**

Patients will be asked to rate mobility and bone pain as below:

- Current mobility
  - Unrestricted mobility
  - Walks with difficulty
  - Walks with orthopedic aid
  - Requires wheelchair
  - Bedridden
- Level of bone pain during the last 4 weeks as
  - None
  - Very mild
  - Mild
  - Moderate
  - Severe
  - Extreme

In addition, investigators will report the number of bone crisis since the previous assessment. Bone crisis is defined as pain with acute onset, which requires immobilization of the affected area, narcotics for relief of pain, and may be accompanied by one or more of the following: periosteal elevation, elevated white blood cell count, fever, or debilitation of >3 days. Category of number of bone crisis defined as:

- No bone crisis
- 1 – 2 bone crisis
- >2 bone crisis

Gaucher disease clinical assessments will be performed at screening and then yearly.

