##### **2.4.4.1.1 Mobility, bone pain and bone crisis**

Category of mobility status and bone pain, as well as number of new bone crises, will be summarized by visit. Absolute value, change from baseline and percent change from baseline of bone crisis over time will be summarized using descriptive statistics by visit using two baselines (study baseline and eliglustat baseline). Additionally, shifts in category of mobility and pain from study and eliglustat baseline by each post-baseline visit will be presented.

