## Appendix B Summary of statistical analyses

### EFFICACY ANALYSIS

Endpoint	Analysis population	Primary analysis	Supportive analysis	Subgroup analysis	Other analyses
Primary endpoints					
Gaucher Disease clinical assessments: Mobility, bone pain, bone crisis	FAS	Descriptive statistics	No	No	No
Bone marrow infiltration	FAS	Descriptive statistics	No	No	No
Bone mineral density (BMD)	FAS	Descriptive statistics	No	No	No
Lytic lesions, osteonecrosis, fractures and infarcts	FAS	Descriptive statistics	Annual incidence rate	No	No
Bone biomarker	FAS	Descriptive statistics	No	No	No
Secondary endpoints					
GD-1 biomarker	FAS	Descriptive statistics	No	No	No

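### The one-record-per-window rule can leave a bone crisis count out of every by-visit row when a final or discontinuation assessment shares a window with a separate annual visit

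*SAP*

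**What the plan says.** SAP 2.1.3.1.1 defines the crisis variable: "In addition, investigators will report the number of bone crisis since the previous assessment". SAP 2.4.4.1.1 gives its analysis: "Category of mobility status and bone pain, as well as number of new bone crises, will be summarized by visit".

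SAP 2.5.4 introduces the windows with "The time window is defined as below to create analysis visit". The notes to Table 2 put the Gaucher disease clinical assessment on Schedule B and add: "Analysis flag will be generated to ensure only one assessment per parameter per analysis visit time window can be included in the analysis". The record closest to target is kept. A tie goes to the scheduled visit, then to the later record. Table 2 has no end-of-study row.

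Protocol 10.2.5.1 repeats the Gaucher clinical assessment at completion or discontinuation. The waiver for recent assessments (Protocol 1.2, footnote b, and 10.2.5.3) covers imaging only. Under Protocol 10.4.3, a patient who stops treatment permanently is assessed with the last-visit procedures if possible, and scheduled follow-up continues.

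On cumulative summaries, the Protocol synopsis says: "For bone disease outcomes, summary statistics as well as cumulative incidence and incidence rates will be calculated, as appropriate". SAP 2.4.4 says: "Cumulative incidence (n, percentage), incidence rate (n/year), or other descriptive statistics will also be displayed as appropriate". In SAP Appendix B, the row "Gaucher Disease clinical assessments: Mobility, bone pain, bone crisis" lists no supportive analysis, whereas the row for lesions and fractures lists an annual incidence rate.

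**The concern.** Keeping one record per window suits mobility (current status) and bone pain (last 4 weeks), because the record set aside is another reading of the same kind of state. A count since the previous assessment is different: the record set aside holds events that no other record contains.

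No other rule rescues it. SAP 2.4.4 refers to 2.5.3 for patients with more than one value in a time frame, but 2.5.3 has no such rule. SAP 2.5.5 on unscheduled visits covers only laboratory data, vital signs and ECG. Nothing says whether a crisis total, if produced, would use flagged records or all records.

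At stake is the completeness of one component of a primary endpoint in a study of approximately 32 patients. The omission may fall on patients who leave because of repeated bone crises, which Protocol 7.3 names as an example of a decline that may warrant discontinuation.

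**Working it through.** **Inputs.** Schedule B windows from SAP Table 2: Week 52 [2, 545], Week 104 [546, 909], Week 156 [910, 1273], Week 208 [1274, 1637]. Target day = 7 × week, giving 364, 728, 1092 and 1456. Annual visits may be up to 14 days early or late (Protocol 10.2.4).

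**Reproducing the windows.** Lower bound = target − 182 (Day 2 for Week 52); upper bound = target + 181. For Week 104: 728 − 182 = 546 and 728 + 181 = 909. All eight annual windows to Week 416 match Table 2.

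**Final-visit days that share a window with an annual visit already held** (Week 52 shown; later windows behave the same way):

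| Annual visit | Exposed final-visit days | Number |
|---|---|---|
| On target (Day 364) | 365–545 | 545 − 364 = 181 |
| 14 days early (Day 350) | 351–545 | 545 − 350 = 195 |
| 14 days late (Day 378) | 379–545 | 545 − 378 = 167 |

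With annual visits on target, the later exposed ranges are Days 729–909, 1093–1273 and 1457–1637.

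**Which count is dropped.** If the annual visit is on target or late, the final visit is always farther from target, so the final count goes. If the annual visit is on Day 350 (distance 14), a final visit on Days 351–377 is closer to target and the annual count goes instead (27 days). Day 378 is an equal-distance tie, settled by scheduled status and then the later date. From Day 379 the final count goes.

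**Planned semiannual days.** Weeks 78, 130 and 182 have targets 546, 910 and 1274. Each is the first day of the next Schedule B window, so a final visit there on target or late has its own row. Held 1 to 14 days early (Days 532–545, 896–909, 1260–1273), it falls back into the window of the annual visit already held.

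**Discontinuation with continued follow-up.** An assessment on Day 600 and a Week 104 visit on Day 728 both lie in [546, 909]. Their distances from target are 128 and 0, so the Day 600 count is dropped, and the count kept runs only from Day 600. On this route the extra assessment can come before the annual visit, so the exemption above for final visits does not carry over.

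**Illustration (assumed counts).** Day 728 reports 1 crisis and a final visit on Day 850 reports 2. The Week 104 row shows 1, which is right for the period to Day 728. The other 2 are in no row. A total from flagged records is 1; the true total is 3.

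**Direction for a rate.** The SAP defines no person-time for crises. Take Day 728 reporting 1 crisis and Day 850 reporting 0, with time counted from Day 1 for simplicity:
- all records: 1 / (850/365.25) = 0.43 per year;
- flagged records, with person-time ending on Day 728: 1 / (728/365.25) = 0.50 per year, which is too high.

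If Day 850 reports 2 instead, all records give 3 / (850/365.25) = 1.29 per year and flagged records give 0.50, which is too low. A summed count can only be too low; a rate can err either way.

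**The case against.** The strongest case against is about size. Planned visits mostly fall on unexposed days: a patient who completes at an annual visit, or on target or late at Week 78, 130 or 182, loses nothing. The study is descriptive, its patients have already had about 4 to 8 years of treatment, and no test or decision uses this count. SAP 2.4.5.1 provides by-patient listings of all treatment-emergent adverse events and of those leading to permanent discontinuation, where crises may be visible.

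All of that stands, and it sets the weight of the point. It does not remove the mechanism, because no text exempts crisis counts from the flag. Nor do adverse event tables replace the counts, since they count repeated events once per patient.

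Three stronger readings are tempting but unsupported:
- *About half of final counts are lost.* 181 of the 364 days after each annual target (49.7%) are exposed, but this is a share of calendar days. It would be a probability only if final visits were spread evenly over the year, and planned visits are not.
- *A promised cumulative crisis analysis lacks its rule.* The synopsis lists crises among the bone disease elements ("The elements of bone disease to be evaluated include bone pain, bone crisis, mobility, bone marrow infiltration"), but cumulative incidence and rates are to be given as appropriate, and Appendix B names none for crises. Such a summary is permitted, not committed.
- *Lost crises vanish from the report.* The loss is from the efficacy summary, not necessarily from the safety listings.

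**Conclusion.** The point holds in a limited form. When a final or discontinuation assessment shares a Schedule B window with a separate annual visit, one of two non-overlapping crisis counts appears in no by-visit row. A crisis total summed from flagged records would then be too low whenever the dropped count is above zero. The direction for a rate depends on how person-time is defined.

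Exposure is confined to off-schedule final visits, discontinuation assessments, and semiannual completion visits held 1 to 14 days early. The documents give neither the distribution of final-visit days nor a crisis rate, so the number of crises lost cannot be estimated and may be zero. The conclusion assumes that the flag is applied as written to crisis counts as to every other Schedule B parameter. It is a minor fix, worth making because a stated rule can drop events from a primary-endpoint summary.

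**What to change.** In SAP 2.5.4 and 2.4.4.1.1, state that the one-per-window flag does not discard bone crisis counts, and add:

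1. **By visit.** Keep the annual assessment's count in its annual row. Show any other post-baseline count in the same window (final, discontinuation or unscheduled) in a separate end-of-study/other row.
2. **Cumulative, if produced.** Sum all post-baseline counts per patient and report the number (%) of patients with any crisis.
3. **Rate, if produced.** Run person-time from the assessment at which the first count starts to the last crisis assessment, so that numerator and denominator cover the same period. The first count reaches back to the preceding assessment, which is before Day 1.

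This needs no crisis onset dates, which the documents do not describe collecting, and no other new data. The cost is a few SAP sentences, minor programming and one extra table row.
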